# b) Visit 3 (BP2) – the PCT visit, 2-3 hours after intercourse and within 27 hours of the CMC:

The participant will return to the clinic 2-3 hours after coitus ends and within approximately 27 hours of the mucus check visit.

- Diary review, AEs, medications, and indications for a directed physical exam, wet mount, and other tests will be managed as described for Visit 2 (BP1).
- The participant will undergo a pelvic exam:
  - o Signs of irritation of the external genitalia, cervix, and vagina, as observed with the naked eye, will be noted.
  - o Cervical mucus will be examined for pH, midcycle characteristics, and the presence of sperm (see **Appendix 2**).

g These will serve as baseline measurements for comparison with those obtained after device insertion during Visit OS1. The alternative would be to collect baseline measurements before device insertion at Visit OS1, but the collection technique (vaginal lavage) is likely to affect subsequent samples taken at that visit.

<sup>h "Other vaginal activity" includes insertion of vaginal medications/products other than the study product (prescription or over-the-counter), as well as insertion of sex toys, fingers, or anything else into the vagina. Tampons may be used during all days of menses in the Baseline PCT and Caya PCT cycles, but only during the first three days of menses in Ovaprene cycles.

Version: 06.00 (FINAL) Date: June 13, 2019

- o Vaginal sample(s) will be collected for pH and the presence of sperm.
- At sites other than EVMS, vaginal samples will be collected for microflora, antibacterial activity, and soluble markers.i
   Baseline PCT results will be interpreted and managed as listed in **Appendix 3**. A successful baseline PCT will show thin mucus containing an average of >5 progressively motile sperm per HPF.
- At the EVMS site only:
  - o 0.5, 1, 2, 4, and 6 hours after the PCT:
    - Cervical mucus will be collected for assessment of pH.
    - Vaginal sample(s) will be collected for assessment of pH.
  - o 6 hours after the PCT, if possible:
    - Vaginal sample(s) will be collected for baseline levels of microflora, antibacterial activity, and soluble markers.k
- The participant will be instructed to refrain from intercourse and other vaginal activity until after Visit BP3, 24 hours after Visit BP2.

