#### 9.4.1 Ovaprene™ Safety Cycle - Visits and procedures:

#### a) Visit OS1, the day following the end of menses (approximately cycle day 6):

- Diary review, AEs, medications, and indications for a directed physical exam, wet mount, and other tests will be managed as described for Visit 2 (BP1).
- Blood will be drawn for CBC, serum chemistries, and serum ferritin.
- The participant will undergo a pelvic exam:
  - o Signs of irritation of the external genitalia, cervix, and vagina, as observed with the naked eye, will be noted.
  - o A colposcopic exam will be completed.

Version: 06.00 (FINAL) Date: June 13, 2019

- o Cervical mucus will be collected for pH.
- o Vaginal sample(s) will be collected for ferrous gluconateo, pH, Nugent score, and microflora.
- o At sites other than EVMS, vaginal samples will be collected for antibacterial activity and soluble markers.
- The participant will insert Ovaprene™ using written instructions, with assistance if needed. The clinician will check the placement.
- At the EVMS site only:
  - o 0.5, 1, 2, 4, and 6 hours after insertion: p
    - Vaginal sample(s) will be collected for ferrous gluconate and pH
  - o At 6 hours after insertion, if possible:
    - Vaginal sample(s) for antibacterial activity and soluble markers will be collected.
- The participant will be instructed to abstain from intercourse and other vaginal activities until after Visit OS5

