# c) Visit OP3, the PCT visit, 2-3 hours after intercourse and within 27 hours of the CMC:

The participant will return to the clinic 2-3 hours after coitus ends and within 27 hours of the mucus check visit.

- Diary review, AEs, medications, and indications for a directed physical exam, wet mount, and other tests will be managed as described for Visit 2 (BP1)
- An acceptability questionnaire will be administered.
- The participant will undergo a pelvic exam:
  - o Signs of irritation of the external genitalia, cervix, and vagina, as observed with the naked eye, will be noted.
  - o The position of the device relative to the cervix will be noted.
  - o Cervical mucus will be examined for pH, ferrous gluconate, midcycle characteristics, and the presence of sperm (see **Appendix 2**).
  - o Vaginal sample(s) will be collected for pH, ferrous gluconate, and the presence of sperm.
  - o At sites other than EVMS, vaginal samples will be collected for antibacterial activity and soluble markers.
  - Results of the test PCT will be interpreted as shown in Appendix 3. A successful test PCT will show mucus containing an average of <5 progressively motile sperm per HPF.
- At the EVMS site only:
  - o At 0.5, 1, 2, 4, and 6 hours after the PCT: u
    - Vaginal sample(s) will be collected for pH and ferrous gluconate.
  - o At 6 hours after the PCT, if possible:

<sup>t "Other vaginal activity" includes insertion of vaginal medications/products other than the study product (prescription or over-the-counter), as well as insertion of sex toys, fingers, or anything else into the vagina. Tampons may be used during all days of menses in the Baseline PCT and Caya PCT cycles, but only during the first three days of menses in Ovaprene cycles.

<sup>u Samples will be collected at as many of these timepoints as possible.

Version: 06.00 (FINAL) Date: June 13, 2019

- Vaginal sample(s) for antibacterial activity and soluble markers will be collected.
- The participant will be instructed to refrain from intercourse and other vaginal activity until after Visit OP4, 24 hours after Visit OP3.

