characteristics and sperm  Cervical mucus by pipette - ferrous		Х	Х		Х	Х							Х	Х			Х
gluconate									Х		Х	Х	Х	Х		Х	х
Replace Ovaprene if displaced									X		X		X	X		X	X
Vaginal lavage - antibacterial activity,											7.			,			
soluble markers		Χ	X 				$X^{11}$	Χ	Х	Х	Х	Х		X 		Х	Х
Remove Ovaprene - swab for staph																	
aureus and store											Χ					Χ	Χ
Colpo exam of cervix under																	
magnification	Х						Χ				Χ	Χ				Χ	Х
Pap Test 	Х									1							
GC/CT if using cervical specimens 	Χ																Χ
Colpo exam of fornices and of vagina																	
(latter while removing speculum)	Х						Х				Х	Х				Χ	Х
Ovaprene Fit Test				Χ													
Caya Fit Test	Х																Х
Insert Ovaprene 							Χ					Χ					Χ
Remove Caya						Χ											Χ
Dispense Caya					Χ												
Explain Trials.ai	Х																
Dispense OPK Kit	Χ			Χ				Χ				Х				Χ	Χ
Dispense condoms	Χ			Χ							0					0	Χ

<sup>1 Medical and Obstetrical history will include contraceptive and gynecological history also.

Version: 06.00 (FINAL) Date: June 13, 2019

<sup>2 A physical exam will be performed if the history is significant for a medical condition. The directed physical exam can be performed at any visit.

<sup>3 HIV testing will be performed on all female participants. HIV testing is available for the male partners, if requested.

<sup>4 Urinalysis is only required if participant is symptomatic for UTI. Treat UTI with oral meds. If Visit 1, continue participant. If after Visit 1, reschedule visit.

<sup>5 The pelvic exam at every visit should look for signs of irritation of the external genitalia, cervix and vagina, as seen with the naked eye. A Pap Test will be performed at Visit 1, if necessary, consistent with the standard medical practice as outlined in the study manual.

<sup>6 **STI**: treat with oral meds and do not continue participant.

<sup>7 **Candidiasis**: treat with oral meds. If Visit 1, continue participant. If after Visit 1, reschedule visit. **BV**: treat with oral meds. If diagnosed at Visit 1, continue participant. If diagnosed after Visit 1, do not continue participant.

<sup>8 EVMS only: Cervical mucus pH will also be tested at 0.5, 1, 2, 4, and 6 hour time points, if possible.

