## 3.2 Subject Disposition

Subject disposition will be summarized for the All Screened population (see Section 3.4 for Analysis Population definitions). The following data will be presented:

- The number and percent of subjects who consented, screen failed, enrolled, treated with Caya®, treated with Ovaprene®, completed or discontinued prematurely from the study. The number and percent of subjects who discontinued for each reason will be presented. Reasons for screen fails will also be summarized categorically.
- The number and percent of subjects at each scheduled visit.
- The number of subjects at each scheduled visit and time point (at hour 0, 0.5, 1, 2, 4, and 6) in the study site at Eastern Virginia Medical School (EVMS).

• The number of subjects who were consented, screen failed, enrolled, treated with Caya®, treated with Ovaprene®, completed, or discontinued at each study site will be presented.

The End of Trial CRF will be used to determine who discontinued prematurely from the study.

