- c) Levels of ferrous gluconate in CVF before sex that are associated with fewer than 5 progressively motile sperm per HPF in the cervical mucus after sex (i.e. success), during ovulation. Summary statistics of sample size, mean, median, standard deviation, and IQR will be presented by visit.
- d) Levels of ferrous gluconate in CVF at multiple time points in the safety cycle in the absence of coitus. This will allow the estimation of how long after insertion it takes to reach the target concentration levels associated with success and whether target levels are still present up to 29 days after insertion. Summary statistics of sample size, mean, median, standard deviation, and IQR will be presented by visit and assessment timepoint.
- e) Levels of ferrous gluconate in CVF before and at multiple time points after sex at ovulation with the device in place. This will allow determination of whether they are different from before sex and, if so, how much time is needed to return to pre-sex levels at all visits in Ovaprene® PCT cycles in both vaginal and cervical fluid. Summary statistics of sample size, mean, median, standard deviation, and IQR will be presented by visit and assessment time-point.
- f) Vaginal pH (from Vaginal Sample CRF) and cervical pH (from Cervical Mucus CRF) before and after sex in the absence and presence of the device. Six-number summary for the observed values and difference between pre-sex and after sex will be presented by visit. For the study site (EVMS only) with multiple timepoints at a visit, the summary will be done at each timepoint. The average of pH values within each visit over the multiple timepoints will be calculated for each subject, and then be summarized. The goal of these assessments during the Ovaprene® safety cycle is to look at the effect of study device in the absence of sex.
- g) Residual amount of ferrous gluconate in Ovaprene® devices that have been worn over a cycle of use. Six-number summary statistics will be presented by visit and by duration of time the device was worn (1-7 days, 8-14 days, 15-21 days, 22-28 days and >28 days).
- h) Cervical mucus score. Summary statistics mean, median, standard deviation, and IQR will be presented by visit. The number and percent of subjects with cervical mucus score ≥ 10 in each Ovaprene cycle will also be presented. For the summary of cervical mucus score ≥ 10, cervical mucus data will only be used from the cycle that occurs after the highest OPK result for that cycle.

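### The within-visit pH average in SAP 3.6 f) misleads in two places at EVMS: vaginal pH at OS1, and cervical pH at BP2 beside OP3

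*SAP*

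**What the plan says.** SAP 3.6, secondary endpoint f), covers vaginal and cervical pH before and after sex, without and with the device. It plans six-number summaries of the observed values and of the pre-sex/after-sex difference, by visit. For EVMS, the only site with serial samples, it adds two summaries:

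- by timepoint: "with multiple timepoints at a visit, the summary will be done at each timepoint";
- by visit average: "The average of pH values within each visit over the multiple timepoints will be calculated for each subject, and then be summarized".

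The next sentence says that pH in the safety cycle is meant to show what the device does in the absence of sex. SAP 3.2 gives the EVMS timepoints: "The number of subjects at each scheduled visit and time point (at hour 0, 0.5, 1, 2, 4, and 6". Hour 0 is therefore one of them.

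The sampling behind these summaries is in the protocol.

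- **OS1 (9.4.1 a).** One vaginal sample, for ferrous gluconate, "pH, Nugent score, and microflora", is listed before the insertion step, and Table 9 places it before insertion. At EVMS, at 0.5 to 6 hours after insertion, "Vaginal sample(s) will be collected for ferrous gluconate and pH". Cervical pH is taken once, before insertion.
- **BP2 (9.2.1 b).** Cervical and vaginal pH are measured at the PCT. At EVMS, at 0.5, 1, 2, 4 and 6 hours after the PCT, "Cervical mucus will be collected for assessment of pH", and vaginal pH is sampled at the same times. Appendix 1, footnote 8, attached to cervical pH at BP2 only, agrees: "Cervical mucus pH will also be tested at 0.5, 1, 2, 4, and 6 hour time points, if possible".
- **OP3 (9.5.1 c).** Cervical and vaginal pH are measured at the PCT. The later EVMS samples are vaginal only: "Vaginal sample(s) will be collected for pH and ferrous gluconate".

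Footnotes in the protocol allow serial timepoints to be missed where collection is not possible.

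**The concern.** An average over a visit is useful when every value in it was taken under the same condition, and when the averages set side by side cover the same times. Neither holds throughout here.

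At OS1, hour 0 is without the device and the later hours are with it. A single average blends the two states that the safety cycle is meant to contrast. For cervical pH, the no-device average at BP2 runs from the PCT to 6 hours after it, while the OP3 average is one measurement at the PCT. Any change in cervical pH over those hours enters one side only.

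At stake is how the reader sees the device's effect on pH, which is a secondary objective (protocol 5.2) for a device designed to release acid (protocol 4). SAP f) also leaves open which EVMS value stands for after sex in the pre-sex/after-sex difference. The visit average is the only single value per woman that f) defines for EVMS, so a programmer could reasonably use it there.

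**Working it through.** The documents state no pH figure, so there is nothing to reproduce. The check counts the planned samples and works out what the averaging rule does to them.

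**Planned EVMS pH values per visit**

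| Measure | OS1 | BP2 | OP3 |
|---|---|---|---|
| Vaginal | 1 before + up to 5 after insertion | PCT + up to 5 | PCT + up to 5 |
| Cervical | 1, before insertion | PCT + up to 5 | PCT only |

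The OS1 mixing therefore concerns vaginal pH only, and the BP2/OP3 mismatch concerns cervical pH only.

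**OS1, vaginal.** Let P be the pre-insertion value, M the mean of k post-insertion values, and include hour 0 in the average.

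Average − P = (P + kM)/(k + 1) − P = [k/(k + 1)] × (M − P)

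If insertion shifts pH by a constant d, then M − P = d, and the share of d that is kept is k/(k + 1).

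| Post-insertion values obtained (k) | Share kept |
|---|---|
| 5 | 5/6 = 83.3% |
| 4 | 4/5 = 80% |
| 3 | 3/4 = 75% |
| 2 | 2/3 = 67% |
| 1 | 1/2 = 50% |

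The dilution is 16.7% with full sampling and 50% for a woman with only hours 0 and 0.5. Because k can differ between women, so can the dilution. With the pre-insertion value kept out, M − P returns the whole of d.

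**BP2 beside OP3, cervical.** Assume no device effect, and let the excess of pH over its pre-sex level be E at the PCT in both visits, with half-life h afterwards. The OP3 value shows E. The BP2 average shows E × S, where S is the mean of 2^(−t/h) over t = 0, 0.5, 1, 2, 4, 6.

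For h = 2: S = (1 + 0.841 + 0.707 + 0.5 + 0.25 + 0.125)/6 = 3.423/6 = 0.571, so OP3 − BP2 = (1 − 0.571)E = 0.429E.

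| Assumed half-life (h) | S | Spurious OP3 − BP2, E = 1.0 | E = 0.5 |
|---|---|---|---|
| 1 | 0.423 | 0.58 | 0.29 |
| 2 | 0.571 | 0.43 | 0.21 |
| 4 | 0.720 | 0.28 | 0.14 |
| 8 | 0.836 | 0.16 | 0.08 |
| 24 | 0.939 | 0.06 | 0.03 |
| flat | 1 | 0 | 0 |

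A linear fall of D over the 6 hours tells the same story. The mean time is 13.5/6 = 2.25 h, so the BP2 average lies (2.25/6) × D = 0.375D below the PCT value.

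The half-lives, E and D are all assumptions. Under a falling pH, the artefact makes OP3 look less acidic than BP2, which would mask an acidifying device effect. With the PCT-time value used at both visits, the spurious difference is zero.

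**BP2 beside OP3, vaginal.** The planned times are identical, so the averages are comparable as designed. They become unequal only where a woman misses different timepoints at the two visits.

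**The case against.** The strongest reply is that SAP f) already supplies the undistorted results. The sentence before the averaging rule requires a summary at each timepoint. Hour 0 against later hours at OS1, and BP2 against OP3 at the PCT, can therefore be read directly. SAP 4.2.3 plans a plot of vaginal pH over collection time at EVMS, and EVMS pH has its own tables, so the site types are not pooled. All of this stands. A reader might infer that the trial's whole assessment of the device's effect on pH is distorted; the documents do not support that, because only the visit-average summary is affected.

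Second, the SAP nowhere says that the averages at BP2 and OP3 will be compared, or that they feed the pre-sex/after-sex difference. This also stands: the side-by-side reading is implied by the endpoint, not written. Likewise, the inclusion of hour 0 is the literal reading, supported by SAP 3.2, but f) does not state it.

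Third, the cervical sizes rest on assumed kinetics and may be zero. Agreed.

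Two other inferences are tempting. One is that the average should be removed altogether. That goes too far, since the vaginal BP2 and OP3 averages are matched by plan. The other is that the hour labels misstate time since intercourse. The protocol counts the BP2 and OP3 serial hours from the PCT and places the PCT 2 to 3 hours after coitus, so this is a separate labelling matter and no part of this point.

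What remains is a stated rule that, followed as written, produces two summaries that cannot be taken at face value.

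**Conclusion.** The point holds in limited form. As written, the within-visit average is not a usable summary of device effect for vaginal pH at OS1, nor a like-for-like summary for cervical pH at BP2 and OP3.

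- **OS1:** 16.7% to 50% of a constant shift is lost, depending on how many post-insertion samples a woman provides. This assumes that hour 0 enters the average and that the average is read against the pre-insertion value.
- **Cervical pH:** the artefact is zero if pH is flat over the 6 hours, and 0.06 to 0.58 units per unit of excess for assumed half-lives of 24 h down to 1 h.

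Severity is minor. The endpoint is secondary and descriptive, no test or success criterion depends on it, the serial data come from one site, and the per-timepoint results remain available.

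**What to change.** Amend SAP 3.6 f) as follows.

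1. **OS1 vaginal pH:** exclude the pre-insertion value from the average, and report the change from it to the post-insertion values.
2. **Cervical pH:** use the PCT-time (hour 0) value at both BP2 and OP3 in place of the average.
3. **Vaginal pH, BP2 against OP3:** for each woman, average only the timepoints obtained at both visits, separately for OP3A and OP3B.
4. **EVMS pre-sex/after-sex difference:** state that the after-sex value is the one at the PCT.

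Keep the per-timepoint summaries and the plot unchanged. The cost is SAP wording and small programming changes, with no new data. The protocol's pH analysis (14.2.3) contains no within-visit average, so no protocol change is needed. The downside is fewer values behind each summary.

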## 3.7 Safety Analysis

All safety analyses will be performed descriptively, and done for the Treated with Caya (if data exists for Caya cycle) and Treated with Ovaprene population.

Except for adverse events and concomitant medication, all safety data summary tables will be based on scheduled visits data, but if an safety assessment was later done again in an unscheduled visit, the data in this unscheduled visit will be used for the summary table in place of the safety data collected at the originally scheduled visit.

#### 3.7.1 Adverse Events

An adverse event is any symptom, sign, illness, or experience that develops or worsens in severity and/or frequency after the date of informed consent. Each AE incidence will be assigned to one of the 3 Study Periods:

- (a) Baseline Cycle,
- (b) Caya® Cycle,
- (c) Ovaprene® Cycles,

depending on the AE start date within the time-frame of:

- (a) from date of consent through Cycle 1,
- (b) during Caya® cycle (Cycle 2),
- (c) in Cycles 3 through 5, respectively.

All adverse events will be coded with MedDRA 20.0. Incidence of adverse events will be summarized by system organ class (SOC) and preferred term (i.e., MedDRA term). The number and percent of subjects with each SOC and preferred term will be presented by the following 2 analysis populations:

- (i) Subject was treated Ovaprene, including AEs at Baseline and Ovaprene cycles
- (ii) Subject was treated with Caya, including AEs at Baseline and Caya cycles

Tables to summarize the incidence rates among female subjects (from those with answer "Female" to the question "Affected person?" in AE CRF) will be created for each of the following groups:

- Overall number and percent of subjects with AEs without presenting SOC or preferred term
- AEs by SOC and preferred term
- Study product-related AEs (including Possibly Related, Probably Related, and Definitely Related) by SOC and preferred term
- AEs presented in descending order of frequency by preferred term (without showing SOC), in which the most frequent one appears at first, and least frequent one will appear in the last
- AEs by SOC and preferred term and by severity
- · AEs by SOC and preferred term and by relationship to the study product
- AEs by SOC and preferred term for each Ovaprene cycle by subgroups of Ovaprene location (based on digital exam) where the following 2 subgroups are used: "Over cervical os", "Not over cervical os". If a subject has an assessment of "Not over cervical os" in the cycle then that will be the classification for that cycle. The "Not over cervical os" will be made up of the following 2 sub-categories: "Not over cervical os - on anterior vaginal wall", and "Not over cervical os and not on anterior vaginal wall".

If a subject reports the same AE (i.e., same preferred term) more than once, that subject is counted only once to each "Study Period", and also only once to the "Total", for the summary of that AE, using the highest severity. The only exception to this will be for the summary by relationship to study device. For that summary, if a subject reports the same AE more than once, that subject is counted only once for the summary of that AE, using the most likely relationship to study product. The same principle will be applied at the body system level summary.

An overall summary of AEs, without presenting SOC or preferred term, by severity and relationship to study product will be presented, where it counts the number of events, not number of subjects, at each and every combination of severity level with relationship level.

AEs that led to premature discontinuation from the study will be listed. Subjects who developed a UTI during the study, as well as SAEs and urogenital system AEs in subjects and male partners will also be listed. These 4 listings will contain the details of those adverse events such as

severity, relationship to study device, and outcome. Other supportive data, such as the subject's age, will be provided. For the listing of "subjects who developed a UTI during the study", it will include the information of medical history of UTI, if any, at the study entry.

